Full Study Protocol and Statistical Plan

Study Title: A Clinical Risk Score for Early Management of TB in Uganda
(NIH/NIAID R21AI161301, PI: [name])

NCT Number: NCT05122624

Date of the document: August 03, 2021

1.SIGNIFICANCE

Tuberculosis (TB) remains the leading cause of mortality, causing over 1.4 million deaths in 2018.¹ A major contributor to TB mortality is underdiagnosis and undertreatment³— particularly in resource-limited primary health clinics. In these settings, up to 40% of patients diagnosed with TB are either lost to care before starting treatment or have treatment substantially delayed.³ Data from our study site in Kampala, Uganda, confirm this finding:¹³ 45% of patients who test positive for TB by Xpert MTB/RIF (“Xpert”, Cepheid, Inc., Sunnyvale, CA, USA) remain untreated one week later. Patients who are diagnosed with Xpert-positive TB and yet remain untreated are at great risk of both transmission and mortality.¹⁴ Many of these infections¹⁵ and deaths¹⁶ could be averted if TB treatment were initiated on the same day as initial presentation.

The most straightforward way to provide same-day TB treatment initiation is to offer same-day microbiological diagnosis, as recommended by the World Health Organization (WHO).¹⁷ Point-of-care Xpert testing shortens time to treatment^{18,19} and in rural Malawi,²⁰ reduced all-cause mortality among patients newly diagnosed with advanced HIV. Similarly, same-day testing and treatment initiation for HIV has been demonstrated to improve patient outcomes, both short-term (e.g., >25% increase in 3-month linkage-to-care)²¹ and longer-term (e.g., 18% increase in 12-month viral suppression)⁴, relative to testing with delayed treatment initiation. However, implementation of same-day Xpert testing is not feasible in many highly resource-limited settings, which often lack the necessary infrastructure and financial resources.^{14,22-24} In these settings, confirmatory TB testing may take days to weeks, and the risk of pre-treatment loss-to-follow-up is high.^{3,25} If global targets (e.g., 90% TB mortality reduction by 2035)²⁶ are to be met, there is therefore an urgent need to improve TB management in these most-resource-constrained clinics where same-day microbiological testing is infeasible.

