3.3.2. Study overview

The overall goals of this proposal are to estimate the effectiveness of the PredicTB clinical risk score in improving clinical outcomes for patients with pulmonary TB and to generate pragmatic data regarding the implementation of this score in highly resource-constrained primary health clinics. If successful, this study will provide an evidence base to justify the design and conduct of a larger cluster-randomized trial. This study will be conducted as a type 2 hybrid effectiveness-implementation evaluation. Our primary effectiveness outcome will be the difference in the proportion of adults with bacteriologically confirmed pulmonary TB who initiate treatment within 7 days of submitting sputum for TB diagnosis, comparing the 12 months before implementing

the PredicTB score to the 12 months after implementation. Secondary analyses will assess for the potential that measured differences reflect improved general practice and/or secular trends. Our primary implementation outcome will be the proportion of patients in the study clinics in whom the PredicTB score is used as indicated. Our study will consist of four phases (Figure 2): pre-implementation, implementation, post-implementation, and end phase. We will adopt a highly pragmatic study design in which we minimize involvement of study staff in the clinics under evaluation, with the exception of the intervention itself.

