3.3.3. Study procedures

[figure not shown]
In the pre-implementation phase

(month -6 to month 6), study and comparison clinics (selected as already having high-quality TB records) will continue to maintain standard TB registers. These registers include all individuals who have sputum sent for TB diagnosis with sputum smear and/or Xpert ("presumptive register") and all individuals who are started on TB treatment ("treatment register"). We will abstract key data from these registers, including age, sex, prior TB treatment, HIV status, diagnostic result, and treatment outcome. During month 1 of the study, we will initiate a retrospective abstraction of all registers from month -6. We will also begin prospective abstraction of registers by having routine clinic staff take photos of registers and securely transfer them to our study team, who will upload these into a REDCap database. Staff from the XPEL-TB trial⁴⁴ have experience in these procedures (including the development of a pre-existing database for this purpose), so we will be able to initiate this abstraction rapidly and seamlessly.

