3.3.4. Analysis Plan

Table 1. Overview of Analysis Plan

Specific Aim	Analytic Goal	Primary Outcomes (1° outcome underlined)	Secondary Analyses	Analytic Strategy
Aim 1	Evaluate PredicTB Effectiveness	Differences in proportions (pre-post): Treatment initiation (1a) Mortality (1b) Loss to follow-up (1b) Difference in differences (study – comparison) (1c)	Adjustment for age, sex, HIV status, treatment history Regression discontinuity	Mixed-effects log-binomial models (clinic as random effect) Parametric regression discontinuity analysis Difference-in-difference ("product term") model
Aim 2	Evaluate PredicTB Implementation	Reach (2a): % same-day empiric treatment Adoption (2b): % providers using PredicTB Implementation (2c): % of encounters using PredicTB as indicated Maintenance (2d): chg in effectiveness over time	Validation with patient surveys Sensitivity/specificity of empiric tx decisions Association with patient level characteristics	Binomial distribution & confidence intervals w/ clustering by clinic Mixed-effects log-binomial models
Aim 3	Estimate PredicTB Impact & Cost-Effectiveness	Projected reduction in 5-year TB mortality (3a) Incremental cost per DALY averted (3b)	Probabilistic sensitivity analyses Uncertainty analyses Unit cost estimation	Markov state-transition model Cost-effectiveness analysis

Aim 1. Evaluate the effectiveness of the PredicTB clinical risk score on clinical outcomes. Our primary analysis will estimate the absolute difference in the proportion of patients with microbiologically confirmed TB (Xpert or smear; study-driven culture results will be excluded) who are initiated on anti-TB treatment within 7 days of submitting an initial sputum specimen for TB diagnosis, comparing the post-initiation period to the pre-initiation period (dark minus light blue in Figure 2). We will estimate this quantity using a multilevel log-binomial

model, with random-effect terms corresponding to each of the four study clinics. We will perform similar analyses for the proportion of patients with TB who complete treatment and die from any cause (Aim 1b).

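### Aim 1b names no death source for confirmed patients who never start treatment and no common follow-up window; the two gaps bias the pre-post mortality comparison in opposite directions.

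*Combined protocol and SAP*

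**What the plan says.** Section 3.3.4 sets the primary analysis (Aim 1a) in microbiologically confirmed patients, with a horizon of 7 days from sputum submission. Aim 1b then gets one sentence: "We will perform similar analyses for the proportion of patients with TB who complete treatment and die from any cause". It states no horizon. Table 1 describes Aim 1b differently: it lists mortality and the entry "Loss to follow-up (1b", but not completion.

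The data come from two routine registers (section 3.3.3). The presumptive register covers everyone with sputum sent for TB diagnosis. The treatment register covers a narrower group: "and all individuals who are started on TB treatment". On content, the plan says: "We will abstract key data from these registers, including age, sex, prior TB treatment, HIV status, diagnostic result, and treatment outcome". Section 3.3.2 intends to "minimize involvement of study staff in the clinics under evaluation". The available text, which lacks the part of section 3 before 3.2, describes no tracing of confirmed patients who never start treatment.

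On timing, the pre-period is months -6 to 6 and the post-period months 7 to 18. The Aim 1 analysis is completed in months 19 to 24. The end-phase activities do not mention further register transfer, and no data lock is given. Section 1 puts TB treatment at six months or more.

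**The concern.** Of the fields named, only treatment outcome could carry a death, and such a field would normally exist only for patients who started treatment. Section 1 says that Xpert-positive patients who "remain untreated are at great risk of both transmission and mortality". If their deaths are missed and PredicTB brings more patients into treatment, deaths move from an unobserved group to an observed one. Recorded mortality can then hide part of a true fall, or even rise.

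The open-ended follow-up works the other way. Patients who enter late in the post-period have had less time in which to die or complete treatment than any pre-period patient, so an early lock exaggerates a mortality fall and understates completion.

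Aim 1b stands under primary outcomes in Table 1, though it is not the underlined one. It is the patient-outcome part of the case that, if successful, "this study will provide an evidence base to justify the design and conduct of a larger cluster-randomized trial". A reader could take a change in recorded mortality, or its absence, as evidence about benefit when it partly reflects recording and the lock date.

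**Working it through.** **The plan's own figure.** Aim 1b has none. For Aim 1a, 550 per period with design effect 1.67 gives 550/1.67 = 329 effective patients. At two-sided 5% (assumed), power for 55% against 66% and 70% is 82.5% and 97.9%, or 80.3% and 97.5% with continuity correction. This agrees with the stated 80% and 97%.

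**Gap 1: deaths before treatment.** Let p be the share ever treated, mT and mU the death risks if treated and untreated, and a the share of untreated deaths that reach a register, with mU and a equal in both periods.

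- True mortality = p·mT + (1 − p)·mU
- Recorded mortality, all confirmed patients = p·mT + a·(1 − p)·mU
- Recorded change minus true change = (1 − a)·mU·(p1 − p0), whatever happens to mT

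The documents give no death risks and no share ever treated. Assume mT = 5%, mU = 20% and p rising from 90% to 95%.

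- True: 0.90×5 + 0.10×20 = 6.50%, then 0.95×5 + 0.05×20 = 5.75%; change −0.75 points.
- a = 0: 4.50% to 4.75%; change +0.25, gap 1.0 point.
- a = 0.5: 5.50% to 5.25%; change −0.25, gap 0.5 point.
- The record rises only if a is below mT/mU = 0.25; above that, the fall is understated.
- mU of 10% to 30% with a = 0: gap 0.5 to 1.5 points.
- mT also falling from 5% to 4%, a = 0: true −1.70, recorded 0.95×4 − 4.50 = −0.70; the gap is still 1.0.
- No rise in share ever treated: gap zero.
- Treated-only denominator, mT unchanged: recorded change 0 against a true −0.75, because the benefit of treating more patients drops out.

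**Gap 2: follow-up.** Take post-period entry as uniform over elapsed months 6 to 18 and deaths as uniform over six months. With lock L, the share of patients with a full six months is (L − 12)/12, and the share of deaths captured is the mean of min(1, (L − entry)/6). Every pre-period patient has at least six months at any of these locks.

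| Lock (end of month) | Full six months | Post-period deaths captured |
|---|---|---|
| 18 | 50% | 75% |
| 21 | 75% | 94% |
| 22 | 83% | 97% |
| 24 | 100% | 100% |

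Because treatment lasts at least six months, the second column is also a ceiling on the share of post-period patients who could have completed it by the lock.

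**Both together** (p 90% to 95%, a = 0, true change −0.75):

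- Month 18: 4.75×0.75 − 4.50 = −0.94, fall overstated
- Month 21: 4.75×0.9375 − 4.50 = −0.05, fall nearly hidden
- Month 22: 4.75×0.972 − 4.50 = +0.12, sign reversed
- Month 24: +0.25, sign reversed

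**Against sampling error.** Borrowing the 1.67 design effect, which was stated for initiation, full ascertainment gives an SE of √[(0.065×0.935 + 0.0575×0.9425)/329] = 1.87 points for a true fall of 0.75. Power is about 7%. With gap 1 alone, a nominal 95% interval covers the true change about 91% of the time at a = 0 and 94% at a = 0.5.

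**The case against.** Several objections carry weight.

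- **Pre-treatment deaths may be recorded.** The field list is introduced as non-exhaustive, so some capture is possible. This stands: missing deaths are an inference, and half capture halves the gap.
- **PredicTB may only bring starts forward.** The primary endpoint is speed, and no document figure gives a rise in the share ever treated. Section 1 pools two groups, patients who "are either lost to care before starting treatment or have treatment substantially delayed". If starts are only earlier, gap 1 vanishes; gap 2 remains.
- **The denominator is not settled.** The wording could mean treated patients only. The formula then does not apply, but the estimate misses the gain from treating more patients.
- **Aim 1c could correct this.** For gap 1, difference-in-differences leaves mU × (study rise − comparison rise): with a 5-point study rise, 1.0 point if comparison clinics do not rise and 0 if they rise equally. All eight clinics are trained and receive feedback, so some shrinkage is plausible. Gap 2 largely cancels there if both groups share the lock and have similar mortality. Aim 1c is not the primary analysis.
- **Mortality is underpowered anyway.** True; a null result would be likely even with perfect data.

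A reader might go further and put 55% to 66% into the formula as the share ever treated, giving a gap of 0.20×11 = 2.2 points and interval coverage of 62%. The documents do not support that: 55% is the share starting within 7 days, only a floor for the share ever treated.

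**Conclusion.** The concern holds in limited form. Aim 1b lacks a vital-status source for never-starters, a fixed window, a lock and a settled denominator. The first gap understates a mortality fall, by about 0.5 to 1.0 point under the assumed 20% untreated risk, 5-point rise and half to no capture, and by nothing if the share ever treated does not change. The second exaggerates a fall and understates completion unless the lock is at about month 24, which leaves no analysis time in the 24-month plan.

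A reader might infer that both gaps hide benefit, or that recorded mortality will rise. Neither follows: the gaps oppose each other and the net sign depends on an unstated lock. Nor is the main result compromised. Seven-day initiation is unaffected, and Aim 3 takes its TB mortality probabilities from the literature. The mismatch between text and Table 1 needs no assumption, but is a matter of reconciliation.

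**What to change.** 1. Use one fixed window from sputum submission in both periods, for example six months. State the lock and continue register transfer into months 19 to 24.
2. For Aim 1b only, include patients whose window closes before the lock, and apply the matching calendar restriction to the pre-period. Keep all 12 months per period for Aims 1a and 2d.
3. For all confirmed patients, report mutually exclusive categories: no treatment-register entry, died on treatment, lost, and still on treatment or completed.
4. Report register deaths as on-treatment mortality, with treated patients as the denominator. Make no all-cause mortality claim for all confirmed TB unless never-starters' vital status is obtained equally in both periods; otherwise show bounds over stated untreated risks and capture shares.
5. Make any composite secondary. If it counts no treatment entry, death and loss as unfavourable, and on-treatment risk u is unchanged, its change is −(1 − u)(p1 − p0): −4.25 points at an assumed u of 15% and a 5-point rise. That is driven wholly by initiation, and the plan should say so.
6. If completion is kept, give it a longer window; each extra month costs a further twelfth of each period. Reconcile the text (completion, death) with Table 1 (mortality, loss to follow-up).

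**Cost.** SAP wording plus continued register photos; section 3.3.5 describes record abstraction as needing few resources. A month-22 lock with a six-month window drops 550×2/12, about 92 patients per period (17%), widens SEs by √(12/10) = 1.095, or about 10%, and leaves two months for analysis. The late post-period is lost for Aim 1b, and deaths among never-starters stay unmeasured unless they are traced.

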In the **implementation phase** (month 7), we will train clinic staff in all eight clinics (study clinics and comparison clinics) on the Ugandan standard of care for diagnosis and treatment of TB. In addition, in the four study clinics, we will provide training on the PredicTB score. This training will include the following elements: (a) background on the PredicTB score and its aim of informing empiric treatment decisions for adult pulmonary TB; (b) provision of materials (paper score sheets and laminated instruction sheets) to enable clinicians to use the PredicTB score; (c) reinforcement that all treatment decisions are ultimately at the discretion of the treating physician; (d) reinforcement that PredicTB is not meant to be a replacement for microbiological testing – that sputum should be sent for microbiological testing in all patients presenting with symptoms of TB, and that any patient with a positive microbiological test should be treated for TB. Prior to this training, we will speak with the head (in-charge) physician at each of the four study clinics to describe the PredicTB score and elicit the physician's recommendations as to the percentage of TB tests that are positive in the clinic (i.e., columns in Figure 1) and the score that should be encouraged as a threshold for same-day empiric treatment initiation. Importantly, this threshold may vary from one clinic to another; our analyses will not explicitly incorporate this threshold as a covariate, but we will explore clinic-by-clinic variation by way of informing any future clinical trial. Furthermore, we will seek the in-charge physician's advice regarding an alternative approach in which patients with high (e.g., >40%) risk could be scheduled for a full treatment course, whereas those with intermediate (e.g., 10-40%) risk could be prescribed a provisional (e.g., 14-day) course, which could be discontinued if microbiological testing for TB was negative and the clinical course [e.g., full resolution in 1-2 days or continued worsening of symptoms despite TB therapy] were inconsistent with a diagnosis of TB. Training in the use of the PredicTB risk score in each clinic will therefore follow the recommendations of each clinic's in-charge physician and will only augment (not supplant) the Ugandan standard of care for TB management. We will re-evaluate these recommendations every three months during site visits (see below) and update training as needed.

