This analysis is subject to bias resulting from both secular trends and non-intervention-related effects. We will therefore also perform a difference-in-differences analysis, comparing pre-post effects in the study clinics to those observed in the comparison (non-PredicTB) clinics (Aim 1c). We have not made this our primary analysis because the comparison clinics are smaller (thereby reducing power) and not randomly allocated – for example, staff in these clinics may be less motivated to change behavior. We will also perform a parametric regression discontinuity analysis to estimate the causal effect of implementing the PredicTB risk score (with the discontinuity occurring at the time of implementation). This analysis, however, has less statistical power, and the shape of the effectiveness curve over time in the post-implementation period may reflect important effects (i.e., we are interested not only in the immediate effect of the intervention but also its maintenance over time).

Sample size considerations. Based on patient volumes in 2019, we anticipate a sample size of 1100 patients with confirmed TB: 550 pre-intervention and 550 post-intervention. Using data from our STOMP-TB study,¹³ we expect that 55% of patients will initiate treatment within 7 days in the pre-intervention period. Assuming a design effect of 1.67 due to clustering by clinic, we will have 80% power to detect a difference if treatment initiation increases to 66% in the post-intervention phase and 97% power if treatment initiation increases to 70% (Figure 3).

[figure not shown]

Figure 3. Study power

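### The study-clinic discontinuity estimates PredicTB plus standard-of-care training, not PredicTB alone, and a partly exposed month 7 tilts its jump and slope

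*Combined protocol and SAP*

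**What the plan says.** **The discontinuity analysis.** Section 3.3.4 (Aim 1) plans a parametric regression discontinuity "to estimate the causal effect of implementing the PredicTB risk score (with the discontinuity occurring at the time of implementation". Table 1 lists it among the secondary analyses: "Adjustment for age, sex, HIV status, treatment history Regression discontinuity". The limits that the plan gives for it are lower power and the shape of the effect over time, on which it adds that "we are interested not only in the immediate effect of the intervention but also its maintenance over time". Neither the text nor Table 1 names the clinics that enter this model.

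**What happens at the break.** Section 3.3.3, implementation phase, reads: "month 7), we will train clinic staff in all eight clinics (study clinics and comparison clinics) on the Ugandan standard of care". It continues: "In addition, in the four study clinics, we will provide training on the PredicTB score". Quarterly visits in the post-implementation phase then bring performance feedback to all clinics.

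**How month 7 is used.** Section 3.3.3 makes month 7 the implementation phase and also the first month of the post-implementation phase (months 7 to 18). Under Aim 2, section 3.3.4 defines maintenance as the change in effectiveness from month 7 to month 18.

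**Safeguards.** On the primary pre-post comparison the plan is open: "This analysis is subject to bias resulting from both secular trends and non-intervention-related effects". It answers with a difference-in-differences analysis, "comparing pre-post effects in the study clinics to those observed in the comparison (non-PredicTB) clinics (Aim 1c", and says of the comparison clinics that "staff in these clinics may be less motivated to change behavior". Section 3.3.2 adds that secondary analyses will look at general practice improvement and secular trends as explanations.

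**The concern.** A discontinuity in time credits the jump to whatever changes at the break. Here two things change in the study clinics in the same month, and only one of them is PredicTB. A study-clinic fit cannot tell them apart, so the causal label claims more than the estimate can carry. The plan's caveat about non-intervention effects is attached to the pre-post analysis, and the limits stated for the discontinuity do not mention the simultaneous training.

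The second point concerns the same break. If clinics are still being trained during part of month 7, that month is only partly exposed, yet it anchors both the fitted jump and the maintenance window. A constant effect would then look like one that starts smaller and grows, and a modest loss of effect could look flat. The text gives no rule for this.

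The study is meant to inform whether a cluster-randomised trial of the score is justified. Crediting the score with a training effect, or reading partial exposure as growth, would blur that decision.

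**Working it through.** **Inputs.** From section 3.3.4: 550 patients per period, 55% starting treatment within 7 days before implementation, 66% or 70% after, design effect 1.67. From sections 3.3.2 and 3.3.3: 12 months in each period. Assumed: two-sided 5% test, even accrual, the design effect carried into the segmented model, and a linear segmented model (intercept, month, post, post × months since month 7).

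**1. The plan's own power.** Effective n = 550/1.67 = 329.3 per period. Power = Φ[(d − 1/n − 1.96·SE0)/SE1], with SE0 pooled and SE1 unpooled.
- 55% v 66%: SE0 = √(2 × 0.605 × 0.395/329.3) = 0.0381; SE1 = √((0.2475 + 0.2244)/329.3) = 0.0379; power = Φ(0.853) = 80.3%.
- 55% v 70%: 97.5%.

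These match the stated 80% and 97%.

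**2. Joint effect.** Let training add s and PredicTB add p, both starting at month 7 and lasting. The study-clinic series steps by s + p, and the fitted jump is s + p. A total of 11 points gives the same jump whether the split s/p is 0/11, 3/8, 5.5/5.5 or 11/0. The difference-in-differences returns (s + p) − s′, where s′ is the training effect in the comparison clinics. It equals p only if s′ = s, and the same holds for feedback.

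**3. Precision of the study-clinic model.** Monthly effective n = 329.3/12 = 27.4; monthly variance = 0.2475/27.4 = 0.00902. For 12 equally spaced months the sum of squares is 143.
- Level-change SE = √(0.00902 × [1/12 + 6.5²/143 + 1/12 + 5.5²/143]) = √(0.00902 × 0.6737) = 7.8 points.
- Slope-change SE = √(0.00902 × 2/143) = 1.12 points per month.

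The plan gives no size for s. If PredicTB did nothing and s were 3, 5 or 8 points (assumptions), the jump would be significant in the upper tail in about 6%, 9% or 18% of studies, against a nominal 2.5%. The fault is therefore mainly in the estimate and its label.

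**4. Partial exposure in month 7.** Month 7 has weight 1/12 + 5.5²/143 = 0.295 in the post-period intercept and −5.5/143 = −0.0385 in the slope. For a constant 11-point effect and month-7 exposure e, jump = 11 − 0.295 × 11 × (1 − e) and false slope = 0.0385 × 11 × (1 − e).

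| Month-7 exposure (assumed) | Jump | False slope per month | Fitted rise, months 7 to 18 (11 × slope) |
|---|---|---|---|
| full | 11.0 | 0 | 0 |
| half | 9.4 | 0.21 | 2.3 |
| none (bound) | 7.8 | 0.42 | 4.7 |

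The half-exposed shift in the jump is 1.6/7.8, about 0.2 SE. The half-exposed slope is 0.21/1.12, about 0.2 SE.

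**5. Leaving month 7 out.** The jump returns to 11.0 and the slope to 0. With 11 post months (sum of squares 110, mean distance from the break 6), level-change SE = √(0.00902 × [0.3788 + 1/11 + 36/110]) = 8.5 points and slope-change SE = √(0.00902 × [1/143 + 1/110]) = 1.20. About 550/12 = 46 patients are lost.

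**6. Pre-post power at 66%, by the formula in step 1.**
- Half exposed: d = 0.11 × 11.5/12 = 0.105, power 77%.
- Wholly unexposed: d = 0.11 × 11/12 = 0.101, power 73%.
- Month 7 left out (550 v 504): power 78%.

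**The case against.** **Implementing may mean the whole package.** Section 3.3.3 describes the implementation phase as standard-of-care training plus PredicTB training, so the causal wording could cover both. This does not stand: the comparison clinics get the same standard-of-care training in the same month, and the plan calls them non-PredicTB clinics.

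**The plan already handles the confounding.** Much of this stands. Aim 1c uses clinics that receive the same training and feedback, Table 1 places it among the primary outcomes and the discontinuity among the secondary analyses, and the pre-post caveat is explicit. A reader might infer that the plan overlooks training effects or that its primary analysis is undermined; the documents do not support that. What remains is the label on the discontinuity estimate, and Aim 1c's reliance on equal training effects, which the plan's own remark on motivation puts in doubt.

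**The clinic set is clear enough.** Probably so: only study clinics implement PredicTB, and comparison clinics are named where they are used. But that reading is exactly the one that produces the joint effect.

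**Month 7 is overstated.** A reader might infer that its two phase labels contradict each other. They do not: months 7 to 18 are exactly the stated 12-month post window. The text gives no training date within the month, and Figure 2 was not available for this check, so no exposure at all is an extreme bound. A reader might also infer a false 11-point gain in maintenance. That needs both the extreme bound and a direct month 18 minus month 7 contrast, which Table 1 does not require (it describes change over time, with mixed-effects models). Such a contrast would have an SE of about √(2 × 0.00902) = 13 points.

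**Conclusion.** The point holds as a limited one about secondary results. A study-clinic discontinuity estimates PredicTB plus standard-of-care training, whatever the split, and should not be reported as the causal effect of the score. Aim 1c isolates PredicTB only under equal training and feedback effects in the two clinic groups. The size of the training share is unknown because the documents give no training effect.

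Partial exposure in month 7 biases the jump down and the slope up: by 1.6 points and 0.21 points per month if half exposed, and by at most 3.2 points and 0.42 points per month, for a constant 11-point effect. The directions are certain under the linear model; the sizes rest on assumed exposure, even accrual and the carried-over design effect, and they are small against the standard errors. The stated power of the primary comparison reproduces, and neither that analysis nor its 12-month window needs to change.

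**What to change.** 1. In section 3.3.4, Aim 1, describe the study-clinic discontinuity estimate as the effect of the month-7 package (PredicTB plus standard-of-care training). Report Aim 1c beside it as the analysis that isolates PredicTB, and state its assumption that training and feedback work equally in both clinic groups. This costs wording only.
2. Keep the 12-month primary window and add a sensitivity analysis that leaves month 7 out of the pre-post, discontinuity and maintenance analyses. This costs about 46 patients, compares 12 calendar months with 11, and raises the level-change SE from 7.8 to 8.5 points.

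An eight-clinic controlled discontinuity is optional and descriptive only. If the comparison clinics supply 400 or 200 patients per period (an assumption), its SE is 7.79 × √(1 + 550/n) = 12.0 or 15.1 points. The detectable change (2.80 × SE) is then about 34 or 42 points, against 45 points of room above 55%. Aim 1c on the same assumption starts from the pre-post SE of √(2 × 0.2475/329.3) = 3.88 points and detects about 17 or 21 points.

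### The stated power treats the two periods as independent groups deflated by 1.67, but the primary analysis is a before-after contrast in the same four clinics, and the plan does not say which variance its model carries.

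*Combined protocol and SAP*

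**What the plan says.** The sample size paragraph of section 3.3.4 expects "550 pre-intervention and 550 post-intervention" patients with confirmed TB and 55% treated within 7 days before implementation. It continues: "Assuming a design effect of 1.67 due to clustering by clinic, we will have 80% power to detect a difference if treatment initiation increases"; the increase named is to 66%, and power at 70% is put at 97%. It attributes the design effect to clustering by clinic and gives neither an intraclass correlation nor a derivation.

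The Aim 1 text says "Our primary analysis will estimate the absolute difference in the proportion of patients with microbiologically confirmed TB" who start treatment within 7 days, "comparing the post-initiation period to the pre-initiation period". Section 3.3.2 confirms that the contrast sets the year before implementing "the PredicTB score to the 12 months after implementation". The Aim 1 model is a multilevel log-binomial "model, with random-effect terms corresponding to each of the four study clinics". Table 1 describes the strategy as "Mixed-effects log-binomial models (clinic as random effect". Neither place names a clinic-by-period term or a method for inference from only four clusters.

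**The concern.** A design effect of the usual kind inflates the variance of a mean, or of a difference between groups made up of different clusters. Here each clinic contributes to both periods. A clinic that is always quick or always slow to start treatment shifts both of its proportions together, so it drops out of the difference. Only variation between clinics in the change adds variance to the pre-post contrast. A clinic intercept removes the first kind of variation and does not represent the second.

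So under the plainest reading of Table 1, the power statement and the planned standard error rest on different variance assumptions. Either the power is understated, or the primary interval is too narrow for the clustering the plan itself assumes. This matters because of how the result will be used: "If successful, this study will provide an evidence base to justify the design and conduct of a larger cluster-randomized trial".

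**Working it through.** **Inputs.** From section 3.3.4: 550 per period, 55% at baseline, 66% or 70% after, design effect 1.67, four study clinics (m = 550/4 = 137.5 per clinic and period). Assumed: two-sided 0.05 (the readable text gives no alpha; Figure 3 is not shown and may state it), equal clinics, risk-difference scale.

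**1. The plan's own figures.** Effective size is 550/1.67 = 329.3 per group. For 55% against 66%, with continuity correction:

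- Difference: 0.11 − 1/329.3 = 0.1070
- Null SE: √(2 × 0.605 × 0.395/329.3) = 0.0381
- Alternative SE: √((0.2475 + 0.2244)/329.3) = 0.0379
- Power: Φ((0.1070 − 1.96 × 0.0381)/0.0379) = 80.3%

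For 70%, the same steps give 97.5%. Without continuity correction, the results are 82.5% and 97.9%. The stated 80% and 97% are therefore correct for two independent groups.

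**2. Clinic intercept, stable clinic differences.** Taking 1.67 = 1 + (m − 1) × ICC gives ICC = 0.67/136.5 = 0.0049. For a within-clinic change, the design effect is D = 1 + (m − 1) × ICC − m × ICC × c, where c is the correlation of a clinic's effect between periods. With c = 1, D = 0.995, so effectively no inflation.

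- 66%: SE = √(0.4719/550) = 0.0293; Φ(0.11/0.0293 − 1.96) ≈ 96%
- 70%: SE = √(0.4575/550) = 0.0288; Φ(0.15/0.0288 − 1.96) ≈ 99.9%

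**3. Clinic intercept, but clinics differ in their change.** The model's SE is too small by a factor √D, so type I error is 2 × (1 − Φ(1.96/√D)).

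| D on the change | Type I error |
|---|---|
| 1.00 | 5.0% |
| 1.17 | 7.0% |
| 1.33 | 8.9% |
| 1.67 | 12.9% |

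D = 1.67 requires c = 0. With c = 0.5, 0.8 and 0.9 (assumed), type I error is 9.0%, 6.5% and 5.7%. If 1.67 was worked out on whole clinics of 275, ICC = 0.67/274 = 0.0024, and D on the change is at most 1.33. At D = 1.67, the implied SD of the clinic-specific change is √(0.67 × 2 × 0.2475/137.5) = 4.9 percentage points.

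Simulated fits of a random-intercept log-binomial model agree: type I error is 4.7% with stable clinics and 12.1% with 1.67 on the change. With unequal clinics (100, 100, 100, 250), a clinic-stratified z test, standing in for the intercept model, runs from 5.0% to 13.0%.

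**4. Clinic-varying period effect, z test.** By simulation with a REML-type variance, power at D = 1.67 is about 79% (66%) and 96% (70%), close to the stated figures. Type I error is 3.7%, 4.9%, 5.8% and 7.6% for D = 1, 1.17, 1.33 and 1.67. With an ML-type variance, it reaches 9.1% at 1.67.

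**5. Four clinic differences, t on 3 df.** The critical value is 3.182. For D from 1 to 1.67, power is about 71% to 51% at 66% and 92% to 76% at 70%, with type I error of about 5%. At 66%, the half-width is 3.182 × 0.0293 × √D, or 9.3 to 12.0 points, against 1.96 × 0.0293 = 5.7 for the intercept model. Even at D = 1 the t test falls well short of step 2, and that part of the loss comes from having 3 df.

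**The case against.** The strongest reply is that the model may already allow effects to vary by clinic. The Aim 1 text uses the plural for its random-effect terms, and the Aim 2 paragraph says random effects will account for implementation effects clustering by clinic. On that reading, the stated power is close to what step 4 gives, and there is no contradiction. This stands as a possible reading. It is not decisive: the second sentence sits under Aim 2, Table 1 names only clinic, and nothing names a period effect that varies by clinic.

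Three stronger readings are tempting, and the documents do not support them.

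- *The study is underpowered.* The direction is not determined. With stable clinics, the plan understates its power.
- *The primary test has a 13% error rate.* That needs both an intercept-only model and the whole of 1.67 on the change, which is the upper end of what the plan's own design effect allows.
- *Clinic-specific thresholds inflate false positives.* The implementation-phase text in section 3.3.3 does let each clinic's in-charge choose a threshold. But if the score has no effect anywhere, differing thresholds create no variation in the change. Under the null, that variation would come from clinic-specific secular shifts. The same text also already plans to explore variation between clinics.

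It is also fair that the study is preliminary. That limits the consequence but does not reconcile the two variance assumptions.

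**Conclusion.** The point holds in a conditional form. Read as a clinic intercept, the model and the power statement cannot both be right. Either 1.67 should go and power is about 96% and 99.9%, or 1.67 describes the change and the planned standard error is too small, with type I error of about 7% to 9% at design effects of 1.17 to 1.33 and at most about 13% at 1.67. If a clinic-varying period effect is intended, the stated power is about right, and the residual issue is a normal critical value with four clinics (about 4% to 8%).

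The sizes rest on two-sided 0.05, equal clinics and an intraclass correlation back-calculated from 1.67. They are illustrations, since the documents give neither that correlation nor the between-period one. The mismatch under the intercept reading does not depend on these assumptions. It affects how firmly the result can be read, not whether the study should run.

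**What to change.** 1. In the Aim 1 text, Table 1 and the sample size paragraph (with Figure 3), make model and power agree. There are two options:
   - Keep the clinic intercept, drop 1.67 and restate power as about 96% and 99.9%, saying that this assumes clinics shift in parallel.
   - Keep 1.67 as variation in the change, add a clinic-by-period random effect to the Aim 1 model, and state its power (about 79% and 96%) with its approximate type I error for four clinics.

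   Either way, state alpha and what 1.67 was derived from.

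2. Keep the mixed model primary. Beside it, as a sensitivity analysis that builds on the clinic-by-clinic exploration already planned in section 3.3.3, report the four clinic-specific pre-post differences with a t interval on 3 df.

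The cost is wording, a recalculated power statement and one more analysis of data already collected. The companion analysis has a wider interval and low power (about 71% to 51% at 66%, 92% to 76% at 70%). Unweighted, it averages over clinics, whereas the primary estimand is a proportion of patients. All of this should be stated in advance. If the intercept model is kept, the primary test's type I error still depends on how far clinics differ in their change.
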